## 1 Introduction

### 1.1 Background

Axial spondyloarthritis (axSpA) is a group of rheumatic disorders with spinal inflammation and inflammatory back pain (IBP) as typical hallmarks. The prevalence of axSpA is up to 1-2% in the Caucasian population ([Braun et al 2011](#)). Patients with chronic back pain (onset before 45 years of age) are classified according to the Assessment of SpondyloArthritis International Society (ASAS) classification criteria for axSpA if they fulfill either the clinical arm or the imaging arm of the criteria ([Rudwaleit et al 2009a](#)).

Patients with axSpA are classified into ankylosing spondylitis (AS) and non-radiographic axSpA (nr-axSpA) based on the presence or absence of sacroiliitis on conventional X-ray radiographs according to the 1984 modified New York diagnostic criteria ([van der Linden et al 1984](#)). Patients with presence of sacroiliitis on X-ray are classified as having AS whereas patients with absence of sacroiliitis on X-ray but presence of inflammatory lesions in the sacroiliac joints (SIJ) on a magnetic resonance imaging (MRI) scan may be classified as having nr-axSpA.

Studies and registry data have shown that patients with nr-axSpA have a similar burden of disease to patients with AS in terms of pain, fatigue and impairment of health-related quality of life (QoL) ([Wallis et al 2013](#)). Disease parameters and response rates to treatment with tumor necrosis factor (TNF) antagonists are similar in patients with AS and nr-axSpA, supporting the concept that axSpA may represent a disease with distinct stages ([Song et al 2013](#)).

The majority of patients with axSpA experience IBP as the first symptom of the disease. According to ASAS criteria, IBP is defined as chronic back pain (lasting longer than 3 months) where 4 out of the following 5 parameters are present: 1) age at onset is below 40 years, 2) insidious onset, 3) causes pain at night with improvement upon getting up, 4) improves with exercise but 5) does not improve at rest. As reported in one study ([Rudwaleit et al 2006](#)), IBP usually improves with the use of nonsteroidal anti-inflammatory drugs (NSAIDs).

Recent studies also demonstrated how spinal pain strongly correlates with QoL measured by the ASQoL questionnaire. Spinal pain also strongly correlates with disease duration and Short Form-36 questionnaire sub-scales ([Bodur et al 2011](#)).

Fatigue is another major clinical feature of rheumatic diseases and is defined as a state of reduced muscle capacity and decreased work ability accompanied by feelings of tiredness, weariness, and lack of energy ([Missaoui and Revel 2006](#)). A recent study by [Bedaiwi et al \(2015\)](#) demonstrated that 67.3% of patients with axSpA had severe fatigue, and that patients with AS and nr-axSpA were equally affected. [Brophy et al 2013](#) demonstrated how fatigue is deeply influenced by pain. In fact, according to the findings of this study, the measures to address fatigue in AS need to focus primarily on the pain rather than anxiety, physical activity, motivation, or sleep. Pain is the single factor examined that contributes to explaining the variation in fatigue. Treatment with anti-tumor necrosis factor therapy may improve levels of pain and fatigue; however, the majority of patients with axSpA may still

experience significant residual pain (mean 54.4 on a scale of 0-100) and fatigue (mean 51.8 on a scale of 0-100) while on treatment.

Secukinumab (AIN457) is a recombinant high-affinity fully human monoclonal anti-human Interleukin-17A (IL-17A) antibody of the IgG1- $\kappa$  class. IL-17A is mainly produced by memory cluster of differentiation (CD)4+ and CD8+ T lymphocytes and is one of the principal pro-inflammatory cytokines in AS as well as other immune mediated inflammatory diseases such as psoriasis, and psoriatic arthritis (PsA). Secukinumab is selective for human IL-17A and potently neutralizes the bioactivity of this cytokine. Secukinumab is marketed as Cosentyx® in more than 60 countries worldwide (including Europe and the US) and is available as solution in different doses for subcutaneous (s.c.) injection. The product is indicated for the treatment of AS (the recommended dose is 150 mg), PsA (the recommended dose is 150 mg; however, for patients who are TNF $\alpha$  inadequate responders (TNF $\alpha$ -IR) or have concomitant moderate to severe psoriasis, the recommended dose is 300 mg) and moderate to severe plaque psoriasis (the recommended dose is 300 mg).

Secukinumab has demonstrated improvements in total spinal pain compared to placebo in Phase III studies in patients with AS at all time points from Baseline to Week 16, and improvements observed at Week 16 were sustained up to Week 52. Secukinumab also led to greater reductions than placebo with regard to the change from Baseline in functional assessment of chronic illness therapy-fatigue (FACIT-Fatigue®) scale total score at all time points assessed from Week 4 to Week 16. However, besides the insights for secukinumab efficacy generated so far, data derived from a controlled and blinded study with a dedicated primary objective assessing pain levels as a potential decision-maker for further treatment options after a relatively short exposure to secukinumab are currently not available.

## 1.2 Purpose

The purpose of the study is to evaluate the efficacy and safety of secukinumab 150 mg compared to placebo in the early management (Baseline to Week 8) of spinal pain, disease activity, fatigue and predictability of disease flares in patients with axSpA who have an inadequate response to prior NSAIDs. This study will also assess the efficacy and safety of secukinumab 300 mg compared to secukinumab 150 mg from Week 8 to Week 24 in order to assess the potential additional benefits of dose escalation in patients with axSpA.

## 2 Study objectives and endpoints

### 2.1 Objectives and related endpoints

Objectives and related endpoints for the study are described in [Table 2-1](#). Note: the treatment arms referred to in [Table 2-1](#) are defined in Section [5.2](#).

**Table 2-1 Objectives and related endpoints**

Objectives	Endpoints

Primary objective
 
 
To assess the superiority of secukinumab 150 mg compared to placebo in achieving a spinal pain score < 4 on a 0-10 numerical rating scale (NRS) at Week 8.
 
	
Primary endpoint
 
 
Proportion of patients with a spinal pain NRS score < 4 at Week 8 in Group A compared to Group B.
 

Secondary objective
 
 
To assess the superiority of secukinumab 150 mg compared to placebo in achieving a Bath Ankylosing Spondylitis Disease Activity Index (BASDAI) score < 4 at Week 8.
 
	
Secondary endpoints
 
 
Proportion of patients with a BASDAI score < 4 at Week 8 in Group A compared to Group B.
 


Exploratory objectives
 
 
Proportion of patients achieving a spinal pain score < 4 on a 0-10 NRS at Week 1, 2, 3 and 4 with secukinumab 150 mg compared to placebo.
 
Proportion of patients in each treatment arm achieving a spinal pain score < 4 on a 0-10 NRS at Week 24.
 
Proportion of patients in each treatment arm achieving BASDAI score < 4 at Week 24.
 
Proportion of patients in each of the treatment arms achieving Ankylosing Spondylitis Disease Activity Score (ASDAS) score < 2.1 at Week 8 and Week 24.
 
Proportion of patients in each treatment arm achieving ASDAS score < 1.3 at Week 8 and Week 24.
 
Mean change from Baseline in functional assessment of chronic illness therapy-fatigue (FACIT-Fatigue®) score in patients on secukinumab 150 mg compared to placebo at Week 8.
 
	
Exploratory endpoints
 
 
Proportion of patients with a spinal pain NRS score < 4 in Group A compared to Group B at Week 1, 2, 3 and 4.
 
Proportion of patients with a spinal pain NRS score < 4 in Arm A1, Arm A2 vs Arm A3, and Arm B1 vs Arm B2 at Week 24.
 
Proportion of patients achieving a BASDAI score < 4 in Arm A1, Arm A2 vs Arm A3, and Arm B1 vs Arm B2 at Week 24.
 
Proportion of patients with a ASDAS score < 2.1 in Group A compared to group B at Week 8 and in Arm A1, Arm A2 vs Arm A3, and Arm B1 vs Arm B2 at Week 8 and Week 24.
 
Proportion of patients with a ASDAS score < 1.3 in Group A compared to Group B at Week 8 and in Arm A1, Arm A2 vs Arm A3, and Arm B1 vs Arm B2 at Week 8 and Week 24.
 
FACIT-Fatigue® score in Group A compared to Group B at Week 8.
 

## 3 Investigational plan

### 3.1 Study design

This is a 24-week, randomized, double-blind, placebo-controlled, multicenter study to evaluate the efficacy and safety of secukinumab in controlling spinal pain in patients with axSpA. The study will consist of 2 treatment periods: a double-blind, placebo-controlled period from Baseline to Week 8 (i.e. Treatment Period 1) and a double-blind secukinumab treatment period from Week 8 to Week 24 (i.e. Treatment Period 2). At Baseline, patients will be randomized to either secukinumab 150 mg or placebo. At Week 8, patients will be re-randomized to 1 of 5 treatment arms to receive either secukinumab 150 mg or secukinumab 300 mg.

Patient eligibility criteria will be assessed during the Screening Period, which will occur for up to 10 weeks prior to randomization.

At Baseline, all patients whose eligibility is confirmed will be randomized in a 3:1 ratio to secukinumab 150 mg or placebo as described below. Patients will be stratified at randomization according to previous exposure to TNF blockers (i.e. according to whether they are naïve to TNF $\alpha$  inhibitors or are TNF $\alpha$ -IR patients) to ensure a comparable number of patients for each subgroup. It is assumed that approximately one third of the randomized patients will be TNF $\alpha$ -IR.

The primary endpoint of this study is spinal pain at Week 8. At Week 8, patients randomized to Group A (secukinumab 150 mg) at Baseline will be assessed as responders (spinal pain NRS score < 4) or non-responders (spinal pain NRS score  $\geq$  4) based on their spinal pain scores. Responders will be re-assigned to 1 treatment arm to continue secukinumab 150 mg (Arm A1) from Week 8 until Week 24. Non-responders will be separately re-randomized to 1 of 2 treatment arms to receive either secukinumab 150 mg (Arm A2) or secukinumab 300 mg (Arm A3) from Week 8 until Week 24. At Week 8, patients randomized to Group B (placebo) at Baseline will be separately re-randomized to 1 of 2 treatment arms to receive either secukinumab 150 mg (Arm B1) or secukinumab 300 mg (Arm B2) from Week 8 until Week 24. A schematic of the study design is presented in [Figure 3-1](#).

#### 3.1.1 Treatment Period 1

At Baseline, patients whose eligibility is confirmed will be randomized to receive double-blind treatment with either secukinumab 150 mg or placebo (3:1) in Treatment Period 1 (Baseline to time of study drug administration at Week 8):

- **Group A:** secukinumab 150 mg (1 x 1.0 mL) s.c. administered at Baseline, Week 1, 2, 3 and 4
- **Group B:** placebo (1 x 1.0 mL) s.c. administered at Baseline and Week 1, 2, 3 and 4

Secukinumab 150 mg and matching placebo will be provided as 1.0 mL pre-filled syringes (PFSS).

### 3.1.2 Treatment Period 2

At Week 8, patients will enter Treatment Period 2 (Week 8 to Week 24). Patients randomized to Group A (secukinumab 150 mg) at Baseline will be assessed for the achievement of spinal pain NRS score and will be classified as responders (spinal pain NRS score < 4) or non-responders (spinal pain NRS score  $\geq$  4). Responders will be re-assigned to 1 treatment arm (Arm A1) to continue double-blind treatment with secukinumab 150 mg every 4 weeks from Week 8 to Week 24 (last dose administered at Week 20). Non-responders will be separately re-randomized to 1 of 2 arms to receive double-blind treatment with either secukinumab 150 mg or secukinumab 300 mg every 4 weeks starting at Week 8 up to Week 24 (last dose administered at Week 20), as follows:

- Patients on secukinumab 150 mg who achieve spinal pain NRS score < 4 at Week 8 will be re-assigned to continue secukinumab 150 mg every 4 weeks (Arm A1)
  - **Arm A1:** secukinumab 150 mg (1 x 1.0 mL) plus placebo (1 x 1.0 mL) administered at Week 8, 12, 16 and 20
- Patients on secukinumab 150 mg who do not achieve spinal pain NRS score < 4 at Week 8 will be re-randomized to continue secukinumab 150 mg every 4 weeks (Arm A2) or to escalate to secukinumab 300 mg every 4 weeks (Arm A3):
  - **Arm A2:** secukinumab 150 mg (1 x 1.0 mL) plus placebo (1 x 1.0 mL) administered at Week 8, 12, 16 and 20
  - **Arm A3:** secukinumab 300 mg (2 x 1.0 mL) administered at Week 8, 12, 16, and 20

At Week 8, patients randomized to Group B (placebo) at Baseline will be re-randomized to either secukinumab 150 mg every 4 weeks (Arm B1) or secukinumab 300 mg every 4 weeks (Arm B2):

- **Arm B1:** secukinumab 150 mg (1 x 1.0 mL) plus placebo (1 x 1.0 mL) administered at Week 8, 12, 16 and 20
- **Arm B2:** secukinumab 300 mg (2 x 1.0 mL) administered at Week 8, 12, 16, and 20

[figure not shown]
During the study, patients will be required to self-administer secukinumab or placebo at all study visits and at home at Week 16 (see [Table 6-1](#) and [Table 6-2](#) for the timing of study treatment administration).

On each treatment day during Treatment Period 1, one s.c. injection with either secukinumab 150 mg or placebo will be administered via PFSs.

On each treatment day during Treatment Period 2, two s.c. injections will be administered via PFSs either as 1 injection of secukinumab 150 mg and 1 injection of placebo, or 2 injections of secukinumab 150 mg. This is necessary to maintain the blind since secukinumab is supplied in 1.0 mL PFSs each containing 150 mg secukinumab, i.e. secukinumab 150 mg is supplied as 1 PFS and secukinumab 300 mg as 2 PFSs. Placebo to secukinumab will be supplied in 1.0 mL PFSs to match the active drug.

Patients will be allowed to continue background medications in accordance with Section [5.5.7](#) (concomitant medications) and Section [5.5.8](#) (prohibited medications). For patients taking NSAIDs, intake will be recorded according to ASAS recommendations for collecting, analyzing and reporting NSAID intake ([Appendix 10](#)).

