### **3.3 Rationale for dosing regimen, route of administration and duration of treatment**

Although nr-axSpA is often regarded as a milder disease compared to AS, it has been demonstrated that the burden of the 2 diseases is similar in terms of pain and activity ([Sieper et al 2013](#)). As a consequence, the dose, dose regimen, formulation and route of administration of secukinumab are the same in these 2 populations.

The dose (150 mg and 300 mg), dose regimen (weekly from Baseline to Week 4, monthly from Week 8 to Week 20), formulation (liquid in PFSS) and route of administration (s.c.) for secukinumab used in this study are supported by the comprehensive AS clinical trial program (including the pivotal Phase 3 studies CAIN457F2305 and CAIN457F2310 ([Baeten et al 2015](#)) and the CAIN457F2320 study) that demonstrated the efficacy, tolerability and safety of secukinumab.

The potential additional benefit of dose escalation from secukinumab 150 mg to 300 mg will be explored during Treatment Period 2 (Week 8 to Week 24) in a proportion of patients assigned to secukinumab 150 at Baseline who did not achieve a response at Week 8. Similarly, a proportion of patients in the placebo group will be assigned secukinumab 300 mg during Treatment Period 2 so as to explore how those patients respond to a higher starting dose of secukinumab.

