## **9.8 Sample size calculation**

To assess the assumed effect size at Week 8, a 43.6% response rate (NRS < 4) is assumed for the secukinumab 150 mg group. This number is derived as an average of the response rates observed in the CAIN457F2320 and CAIN457F2310 studies (Baeten et al 2015). For the placebo group, a response rate at Week 8 of 23.5% (NRS < 4) was selected as assessed in the CAIN457F2320 study. This intermediate scenario takes into consideration a certain likelihood of a relatively high placebo response also in line with data from the TNF $\alpha$  reference studies and the CAIN457F2305 study in addition to the slightly milder course of the disease in the studied population (Baeten et al 2015).

Assuming conservatively a response rate of 23.5% in the placebo group and a response rate of 43.6% under secukinumab 150 mg, 332 patients in total (i.e. 249 patients in secukinumab 150 mg group and 83 patients in placebo group) would be needed under 3:1 (secukinumab: placebo) allocation to achieve 90% power on a (2-sided) 5% significance level. To compensate for drop-out patients or those with protocol deviations, a total of 352 patients (264 in secukinumab 150 mg group and 88 in the placebo group) should be recruited.

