- Proportion of patients in each treatment group with response in spinal pain score < 4 at Week 24.
- Proportion of patients in each treatment group with response in BASDAI score < 4 at Week 24.
- Proportion of patients in each treatment group with response in ASDAS score < 2.1 at Week 8 and Week 24.
- Proportion of patients in each treatment group with response in ASDAS score < 1.3 at Week 8 and Week 24.
- Proportion of patients in Arm 1 with spinal pain score > 6 at Week 12 or Week 24.
- Proportion of patients achieving a spinal pain score < 4 for TNF-naïve patients compared to TNF α -inadequate responder (TNF α -IR) patients at Week 8 and Week 24.
- Proportion of patients with response in spinal pain score < 4 to secukinumab 150 mg at Week 8 maintaining a response at Week 24. Only descriptive statistics will be presented for this endpoint.

The statistical significance of the above endpoints between groups will be analyzed by 95% CI of proportion. P-value will be added if there are enough number of patients available. The following continuous exploratory endpoints will also be summarized descriptively with number of patients (n), minimum, mean, standard deviation, median and maximum.

- Change from baseline in spinal pain score according to previous exposure to tumor necrosis factor (TNF) blockers at Week 1, 2, 3, 4, 8, 12 and 24.
- Change from baseline in total spinal pain score at all time points by each treatment group for each treatment period.
- Change from baseline in total BASDAI score at all time points by each treatment group for each treatment period.
- Change from baseline in ASDAS-CRP at Week 8 and Week 24.

If for a significant number of patients, the assignment to responder and / or non-responder status is incorrect, then a risk analysis may be performed.

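### The Week 24 responder rates for Arms B1 and B2 are neither adjusted for nor split by Week 8 status, which costs some precision and makes them hard to read as response to secukinumab

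*Protocol*

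**What the plan says.** - **Re-randomisation.** Only Group A is sorted by its Week 8 score (Protocol 3.1, 3.1.2, 5.2, 5.3). For placebo patients, Protocol 3.1.2 says: "At Week 8, patients randomized to Group B (placebo) at Baseline will be re-randomized to either secukinumab 150 mg every 4 weeks (Arm B1") or to 300 mg (Arm B2). No Week 8 condition or stratum is given. The only stratification factor stated is TNF-inhibitor history, at Baseline.
- **Aim.** Protocol 3.3 assigns part of the placebo group to 300 mg "so as to explore how those patients respond to a higher starting dose of secukinumab".
- **Endpoint.** Protocol Table 2-1 takes the proportion with spinal pain below "4 in Arm A1, Arm A2 vs Arm A3, and Arm B1 vs Arm B2 at Week 24". It sets the same contrasts for BASDAI below 4 and for the two ASDAS cut-offs. SAP 2.13 lists "Proportion of patients in each treatment group with response in spinal pain score < 4 at Week 24".
- **Method.** SAP 2.13 compares these proportions through a 95% CI, with a p-value if numbers allow. Under Protocol 9.6 any test follows the primary method, and that model (SAP 2.5.2) contains treatment, country and TNF stratum.
- **Use of Week 8 elsewhere.** SAP 2.1.1 makes Week 8 the baseline for Treatment Period 2. SAP 2.11 reports FACIT-Fatigue change from Week 8, and SAP 2.13 reports change in spinal pain and BASDAI by treatment period. These are change scores, not threshold proportions.
- **Maintenance endpoint.** It covers only patients who responded to secukinumab 150 mg at Week 8.
- **Planning rate.** For placebo, Protocol 9.8 says "a response rate at Week 8 of 23.5% (NRS < 4) was selected".

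**The concern.** By the SAP's own definition, Week 8 is where Treatment Period 2 starts for Group B. On the planning assumption, close to a quarter of these patients already meet the Week 24 criterion at that point, without having received any secukinumab. The whole-arm Week 24 rate therefore mixes patients who fell below 4 on secukinumab with patients who fell below 4 on placebo and stayed there. The plan gives no way to tell the two apart in the responder tables.

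Two things are at stake, both exploratory. The B1 and B2 rates are easily read as response to secukinumab when part of them may predate it. The comparison of 300 mg with 150 mg also makes no use of a Week 8 measurement that the trial already collects on every patient.

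**Working it through.** **1. Source of the 23.5%.** Inputs from Protocol 9.8: "a response rate at Week 8 of 23.5% (NRS < 4) was selected"; "a 43.6% response rate (NRS < 4) is assumed for the secukinumab 150 mg group"; 3:1 allocation; "to achieve 90% power on a (2-sided) 5% significance level". With d = 0.436 - 0.235 = 0.201 and pooled rate (0.235 + 3 × 0.436)/4 = 0.386, the uncorrected two-proportion formula gives 77 placebo patients (308 in total). With the continuity correction it gives 83 placebo patients, and 4 × 83 = 332, the protocol's figure exactly. So 23.5% is the rate the trial is sized on. It is an assumption, not an observed share.

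**2. Patients already below 4 at Week 8.** 88 × 0.235 = 20.7, about 21 of Group B. At an assumed 1:1 split, 44 × 0.235 = 10.3 per arm, leaving about 34 per arm at 4 or above. This ignores dropout before Week 8.

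**3. Share of Week 24 responders who predate secukinumab.** Let r = 0.235, s = the proportion of Week 8 responders still below 4 at Week 24, and p = the Week 24 rate in the others. The documents give neither s nor p. The share is r·s / [r·s + (1 - r)·p].

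| p in B1 | s = 0.6 | s = 0.8 | s = 1 |
|---|---|---|---|
| 30% | 38% | 45% | 51% |
| 43.6% | 30% | 36% | 41% |

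**4. Dilution.** If s is the same in both arms (300 mg adds nothing in Week 8 responders), s cancels and the whole-arm difference is (1 - r) = 0.765 times the difference in Week 8 non-responders. So 15 points becomes 11.5, 20 becomes 15.3 and 30 becomes 23.0. For placebo rates of 15% to 35% the factor runs from 0.85 to 0.65.

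**5. Bias.** Simulation of 44 per arm with no dose effect (20,000 runs) gives a mean difference of 0.0 points. Rejection is 4.4% for the unstratified test and 5.1% for a Cochran-Mantel-Haenszel test stratified by Week 8 status.

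**6. Precision.** Assume Week 24 rates of 80% in Week 8 responders and 35% in the others.
- Whole-arm rate: 0.235 × 0.80 + 0.765 × 0.35 = 0.456.
- Unstratified variance per patient: 0.456 × 0.544 = 0.248. Half-width: 1.96 × √(2 × 0.248/44) = 20.8 points.
- Within-stratum variance: 0.235 × 0.16 + 0.765 × 0.2275 = 0.212. Half-width: 1.96 × √(2 × 0.212/44) = 19.2 points.

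**7. Power, all 44 per arm, unstratified v stratified.** Each scenario has a 20-point difference in Week 8 non-responders.

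| Non-responder rates | s | Unstratified | Stratified |
|---|---|---|---|
| 43.6% v 63.6% | 0.9 | 33% | 35% |
| 30% v 50% | 0.9 | 29% | 36% |
| 30% v 50% | 1.0 | 29% | 39% |

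The two tests differ slightly in size (step 5), so the smallest gain should not be over-read. From 43.6%, the smallest difference detectable with 80% power is about 29 points at 44 per arm and about 33 points at 34 per arm.

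**The case against.** The case for leaving the plan alone has real substance.

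- **The question is about all of Group B.** Section 3.3 asks how patients from the placebo group respond, and the whole-arm contrast answers that. This stands. The whole-arm rate should remain the main result, and the 0.765 factor is dilution only relative to the effect in patients still at 4 or above.
- **The SAP does use Week 8.** Period 2 change scores for spinal pain and BASDAI run from the pre-secukinumab value. This stands for change scores. It does not reach the threshold proportions. The repeated-measures model in SAP 2.13 carries a baseline NRS covariate, but the code in SAP 5.4.1 covers visits 2 to 7 only, so its reach beyond Week 8 is unclear.
- **Dilution is conditional.** It requires that 300 mg adds nothing in Week 8 responders, including in keeping them below 4. This stands.
- **A subset is not cleaner.** Patients selected for a score of 4 or more tend to regress to the mean, and there is no concurrent placebo after Week 8. This stands against replacing the whole-arm analysis with a subset, but not against stratifying it.

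A reader might also infer stronger claims that the documents do not support:
- That placebo responders automatically count at Week 24. Nothing carries Week 8 status forward; a patient counts only if below 4 at Week 24.
- That B1 and B2 are unfairly compared with A2 and A3. The contrasts stated are A2 v A3 and B1 v B2.
- That chance imbalance in Week 8 status is an added hazard. It is ordinary sampling error, already inside the ±20.8-point interval.

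**Conclusion.** The point holds as a limit on precision and interpretation in an exploratory contrast. The planned B1 v B2 responder proportions take no account of Week 8 status, although Group B is re-randomised whatever that status is. About 21 of 88 patients would be expected below 4 before their first secukinumab dose. Depending on how many stay there and how the rest respond, 30% to 51% of Arm B1's Week 24 responders could be patients who reached the criterion on placebo (step 3).

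Reading this as a biased dose comparison would go too far: both arms are drawn at random from one pool, and the simulated difference under no effect is zero. The primary and secondary analyses are not affected.

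The gain from a change is modest. The interval narrows by about 1.6 points each side, and power rises by about 2 to 10 percentage points while staying below 40% in the scenarios simulated. These sizes rest on the 23.5% planning rate, 1:1 allocation, no dropout before Week 8, and Week 24 rates that the documents do not give. No placebo planning rate is given for BASDAI or ASDAS, so the size of the effect there cannot be stated.

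**What to change.** In SAP 2.13, for the B1 v B2 contrasts at Week 24:

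1. Keep the all-patient B1 and B2 rates as the main result.
2. Estimate the B1-B2 difference using all patients in both arms, stratified by Week 8 status (below 4, or 4 and above) or adjusted for the Week 8 score. A stratum-weighted risk difference is preferable: an odds ratio adjusted for a strong predictor is not on the same footing as the unadjusted one.
3. Add, as a descriptive supplement, Week 24 response by Week 8 status within each arm.
4. Do the same for BASDAI below 4 and the two ASDAS cut-offs, each with its own Week 8 status.
5. State how a missing Week 8 value is placed in the strata.

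No new data are needed: spinal pain, BASDAI, patient global assessment and hsCRP are all scheduled at Week 8 (Protocol Table 6-1). No change to the IRT is needed. The cost is SAP wording and a few table rows. The supplementary cells are small, about 10 and 34 patients per arm for spinal pain, so they should be shown with intervals and not tested.
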